Patients will be observed for 28 days. All participants should complete their follow-up study visits, including efficacy assessments, safety assessments, vital sign assessments, and blood collection.

Clinical evaluation: A detailed medical history will be obtained by the PI ([name]) or Co-I ([name]). This will include information regarding the subjects' full history of medical and psychiatric conditions, diagnoses, procedures, treatments, demographic information, and any other noteworthy medical information, including suicidality, with dates of start and finish. This information will be collected either in person or virtually. Any updates to medical history information that the PI or designee becomes aware of will be captured throughout the study. The PI's will perform the physical examinations (PEs) as indicated in the Schedule of Events (SOE). A complete PE, including assessments of the skin, head, eyes, ears, nose, throat, neck, thyroid, chest/lungs, heart, abdomen, lymph nodes, extremities, and general appearance. The physical examination will not include a pelvic, breast, or rectal examination. A neurological examination will also be performed, which includes mental status, cranial nerves, strength, sensation, deep tendon reflexes, and coordination.

Vital Signs: Evaluation of vital signs will be performed by qualified site personnel after the subject has been supine for 5 minutes and will include a measurement of systolic and diastolic blood pressure, pulse rate, oral temperature, and respiratory rate. Systolic and diastolic blood pressure should be then measured from supine to standing to assess orthostatic hypotension. Subjects will be asked about lightheaded or dizzy, blurry vision, weakness, syncope, confusion, or nausea why performing orthostatic vital signs. Vital sign measurements will be obtained at the time points indicated in the study flow chart and following the supine ECG assessments, if taken at the same time. Blood pressure should be taken on the same arm throughout the study.

Anthropometric Measurements: Weight (kg) (assessed in ordinary indoor clothing with shoes off) will be recorded at the time points indicated in the flow chart. Height (cm) will be recorded at Visit 1 (screening) only. Body Mass Index (BMI) will be calculated at all visits in which anthropometrics are collected. Waist circumference will be measured to the nearest 0.1 cm.

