SS-OCTA: Images will be obtained using the Zeiss PLEX Elite 9000, which is a quick, inexpensive, and non-invasive method for acquiring retinal images with an axial resolution of ~5µm and a scan depth of 3.0mm. Automated layer segmentation provides four horizontal depth-resolved retinal slabs: superficial (SRL), deep (DRL), outer retinal layer (ORL) and the choriocapillaris. Participant images will be excluded for low signal strength (≤6), blink artifacts, doubling artifacts, media opacity obscuring visualization of the vasculature, and/or segmentation errors. Manual segmentation editing will be conducted to ensure proper layer assessment. Microvessels for the SRL, DRL, and choriocapillaris slab will be processed using a custom semiautomated algorithm we developed to rapidly quantify several vessel parameters including vessel density, length, diameter, and capillary network. All images will be independently analyzed and compared among study subjects by two graders blinded to the group assignment.

Outcome: Primary outcomes include the change in PANSS positive and negative scores (2hrs, 5hrs, 1wk, 2wk, and 4wks) in the SNP group compared to placebo. The secondary outcomes include the change in overall cognition (0hr, 1wk, 2wk, and 4wks) and retinal microvascular measures (0hr, 5hrs), as well as examining the relationship between baseline or change in retinal vessel measures or CRP and the change in psychosis symptoms and cognition after SNP treatment compared to placebo.

SNP Treatment Protocol

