The BIDMC *IV DRUG ADMINISTRATION GUIDELINE* for clinical use of Nitroprusside Sodium (Nipride®) recommends use of this drug in the ICU setting. We are proposing the use of intravenous (IV) SNP for a research study in stable (not hospitalized) patients with early course schizophrenia (Clinical Trials.gov registry: NCT04986072; IND Exemption approved on 8/31/2021). Per our discussions with Critical Care leadership (Drs. [name] and [name]), there are limited intensive care unit (ICU) beds available for research subjects who aren't already admitted to the ICU. It is important to note that five prior clinical trials of SNP in similar populations have also been conducted in non-ICU settings with no adverse effects reported¹-5. For these reasons, we are proposing that the SNP study in early course schizophrenia take place in the Clinical Research Center (CRC) at BIDMC. We have received approval from the Critical Care Executive and Critical Care Practice Committees for execution of the protocol in the CRC at BIDMC (please see attached approval letters).

[name], PhD (Neuropsychiatrist, clinical investigator, and Assistant Professor of Psychiatry at BIDMC/HMS) is the PI for this study. [name] will conduct efficacy and safety assessments, perform medical reviews, recommend medical clearance for study inclusion, and conduct assessments prior to discharge. [name] will be available at the CRC through the study visit.

[name] MD, (Pulmonary and Critical Care Physician, clinical investigator, and Assistant Professor of Medicine at BIDMC/HMS) is the co-investigator, has prior experience with administering SNP, and will be the physician of record for the study. [name] will provide oversight of medical clearance, ordering the study drug, and responding to clinical issues during the study visit. [name] will be available before, during, and after the SNP infusion. Specifically, [name] will be present in the CRC 30 minutes prior to SNP infusion and 30 minutes after the initiation of SNP. [name] will be available on the East Campus of BIDMC after stable titration of SNP, in close to proximity to the CRC.

The **BIDMC CRC** is prepared to support this study and has the appropriate resources to conduct the study, including 1:1 ACLS/BLS certified nursing. CRC nursing staff involved with the study will

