- All side effects and vital parameters will be recorded during the infusion and 2 hours following the infusion by CRC nursing.
- Any abnormal, clinically significant vital signs will be recorded as adverse events.

Discharge Procedure

- Gross motor and cognitive function, ataxia, reflexes/clonus will be evaluated and documented by a study PI ([name]) prior to discharge.
- Before being discharged patients should be awake and alert, feeling well, with no nausea, vertigo, or dizziness.
- There should be no significant change in vital signs from prior to infusion.
- They will be given a small meal before discharge from the CRC.
- Patients will be instructed not to drive. If necessary, the study nurse will release them to the
 care of an adult family member or caregiver, who will accompany the patient home. If
 needed, a trained Research Assistant will contact the participants support system to ensure
 transportation is coordinated.

Study Drug Handling

- Nitroprusside will be compounded by research pharmacy in 5% dextrose
- 5% dextrose will be used as placebo
- Study drug will be stored at room temperature and the required amount will be released from the pharmacy to the CRC at the time a patient is scheduled for the protocol.
- Study drug will be provided in light-blocked bags with labeling to ensure blinding of study staff.

Nitroprusside standard concentration is 50mg/250mL of D5W and the concentrated version is 100mg/250mL.

Institutional Approvals

Critical Care Executive – [name] and [name] – Approval granted on 9/8/21 Critical Care Practice – [name] and [name] – Approval granted on 9/8/21

B. Statistical Considerations

Power calculation: With 16 ECS individuals in the SNP group and 16 in the placebo group we will have >80% power to detect a 10-point PANSS difference between the placebo and treatment groups, with a SD of 6, alpha of 0.05, 2-sided alternative hypothesis, 2-sample t-test, based on the sample size suggested by the retinal vessel differences in our pilot data. The above-mentioned sample size was determined based on our pilot SS-OCTA data, which suggests that we will have >70% power to detect group differences of at least 0.007 (estimated standard deviations of skeletal density =0.008, significance level=0.05, two-sided t-tests).

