Baseline demographic details will be compared between the SNP and placebo groups using independent-samples t tests or Mann-Whitney U tests where appropriate using R software. Categorical data will be compared using chi-square tests. Effect sizes will be provided using Cohen's d. The primary outcome (PANSS) will be analyzed using a 2 (treatment group) × 5 (time point) mixed analysis of variance (ANOVA). Analyses of secondary outcome measures will be compared using a 2-group x 4 time point mixed ANOVA for cognition and a 2 x 2 for retinal measures. The relationship between baseline or change in retinal vessel measures or CRP and change in PANSS scores or cognition will be performed using Pearson's (parametric) or Spearman's (non-parametric) correlation.

C. Subject Selection

Population: Men and women, 18-60 years of age, from diverse background, symptomatic, with early course schizophrenia, and meet all study inclusion and exclusion criteria.

Inclusion criteria for ECS patients are: a DSM-V diagnosis of SZ or schizoaffective disorder with ≤5 years from the onset of psychosis and up to 2 years of lifetime exposure to antipsychotics, total score of ≥55 on the PANSS with a score of ≥3 on 1 or more PANSS Positive Scale items (delusions, conceptual disorganization, hallucinatory behavior, suspiciousness, or unusual thought content) and/or score of ≥3 on the CGI-S scale, taking antipsychotic for 8 weeks with a stable dose of 4 weeks (no medication change will be allowed during the trial), English proficiency, understands and is able, competent and willing to give informed consent in accordance with the International Conference on Harmonization Good Clinical Practice Guidelines.

Exclusion criteria are:

- Presence of renal, hepatic, cardiac, hematologic, neurologic impairments or abnormal physical exam.
- Presence of retinal disease (myopia >4.0 diopters)

- Baseline systolic BP <100mmHg or symptomatic orthostatic hypotension (systolic BP <90 mmHg or diastolic BP <60 mmHg) with any of the following: lightheaded or dizzy, blurry vision, weakness, syncope, confusion, nausea.
- Pregnant or breastfeeding (pregnancy test at screening visit and prior to randomization).
- Abnormal laboratory testing (see appendix)
- Treatment with medications that may interfere with the metabolism or excretion of SNP or are associated with drug-drug interactions (see list of medications below).
- Prior history of intolerance to SNP
- Currently taking clozapine or chlorpromazine

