Psychological Interview: There is a possibility that a patient may become distressed when being asked about symptoms or personal information during the diagnostic evaluation or assessment session. The primary risks to the patients are discomfort or anxiety. Subjects may also experience some discomfort or anxiety from discussing personal information. Yet this anxiety is not expected to be greater than that subjects already experience and subjects will be assured that they will be able to withdraw from the study at any time. There is a possibility of suicidal ideation as a result of any anxiety or distress associated with discussing personal information. This risk is largely reduced by screening out patients with significant suicidal ideation or those who have enacted suicidal behaviors within 6 months prior to intake.

Cognitive Tests: The cognitive tasks pose no risks to participants. The tasks will require sustained attention and mental effort for a steady period of time. This could lead to minor temporary fatigue or boredom, but otherwise there are no known risks. We will ensure that data remain as confidential as possible. Also, these data generally are not considered to be of sensitive nature.

Confidentiality: Although every effort will be effort made to assure confidentiality, it is possible someone could without permission gain access to study related data during the time they are being used or stored for examination results.

Blood draw: Temporary irritation from the needle stick, the likelihood of pain or bruising at the site of the blood draw, occasional symptoms of lightheadedness, and, in rare cases, infection at the site of the blood draw are all risks and discomforts associated with the blood draw procedure.

SS-OCTA: OCTA is painless and safe techniques that will be used to investigate the structure and function of the retina. Performing these imaging techniques in individuals with psychotic disorders does not pose specific, additional unique challenges or risks to the participants. Participants will have their pupils dilated for OCT/OCTA retinal imaging, as is done with all ophthalmology imaging facilities, which may result in light sensitivity or acute angle-closure glaucoma. When possible, we will forgo pupil dilation, especially when high quality retinal images can be obtained without the need for pupillary dilation.

IV infusion of SNP:

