Patients with schizophrenia, schizoaffective disorder may be considered a vulnerable population. The multi-step consent process involving both a phone screening and in-person visit, or secure remote process provide safeguards and opportunities for subjects to understand the study and choose whether or not to partake. Subjects will be questioned to confirm their understanding of the protocol and possible risks or adverse side effects of Sodium Nitroprusside, thus helping ensure that subjects with incomplete understanding do not unwittingly consent to the study. Finally, we will also complete a one-page Assessment of Capacity form to provide informed consent. We will assure subjects both on the informed consent form and in person that refusal to partake in the study or drop-out from the study at any point has no impact on continued services from their current clinic or at BIDMC. Clinical interviews will be performed by a trained clinical staff who will be able to reassure subjects or if necessary, provide counseling if they are distressed. Subjects will be forewarned throughout the pre-screening and screening process that the protocol involves sitting in a chair for up to 5 hours, and that they may take breaks at any time. Breaks will be offered to subjects regularly, though they may decline to take them.

Again, if during the consent process or any study visit, study staff notice the subject expressing suicidality, homicidality appearing agitated or distressed, or if they score 4 or higher on the PANSS question G6 "Depression", they will be instructed to pause the protocol and immediately contact the investigator (Drs. [name] or [name], all trained psychiatrists), who will perform a safety assessment, contacting outpatient providers or emergency services as deemed necessary.

B7. STUDY LOCATION

Privacy

Screening will be performed by phone or via Microsoft Teams and we will assure that the participant is located in a place where they can securely answer any sensitive questions. Initial screening for the study will take place over the phone/Microsoft Teams via a screening questionnaire. At the start

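### The 2 × 5 mixed ANOVA for PANSS has no missing-data rule and conventionally drops anyone with a missed rating; a likelihood-based mixed model would keep the data at almost no cost

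*Combined protocol and SAP*

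**What the plan says.** Section B3.B (Statistical Considerations) gives the primary analysis in one sentence: "The primary outcome (PANSS) will be analyzed using a 2 (treatment group) × 5 (time point) mixed analysis of variance (ANOVA". R is named for the baseline comparisons, but no function or package is given for this ANOVA. The five time points come from section B3.A (Outcome): "Primary outcomes include the change in PANSS positive and negative scores (2hrs, 5hrs, 1wk, 2wk, and 4wks". The sample size is stated as "With 16 ECS individuals in the SNP group and 16 in the placebo group", and section B6 (Recruitment) gives the same total of 32, so there is no allowance for loss.

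No section defines an analysis set, imputation, or a rule for missed ratings or early withdrawal. The nearest text, in section B3.A (Follow up visits), is an expectation about conduct: "All participants should complete their follow-up study visits, including efficacy assessments, safety assessments, vital sign assessments, and blood collection". Withdrawal is foreseen in section B5 ("subjects will be assured that they will be able to withdraw from the study at any time") and in section B6, Subject Protection ("drop-out from the study at any point has no impact on continued services"), with no expected rate.

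**The concern.** A conventional mixed (split-plot) ANOVA needs a complete row of five ratings per person. Someone who attends the infusion day and weeks 1 and 2 but misses week 4 then contributes nothing, although four valid ratings exist. Someone who misses weeks 2 and 4 loses three. The 2 h and 5 h ratings, closest to the drug exposure, go with the rest.

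Each such person is 1 of 16 in an arm. If loss is unrelated to symptoms, the cost is precision. If it is related to symptoms and unequal between arms, the participants left in one arm are a healthier selection and the estimated difference is biased at every time point.

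**Working it through.** **Inputs from the documents.** 16 per arm, SD 6, difference 10, two-sided alpha 0.05, two-sample t-test (section B3.B); five ratings (section B3.A, Outcome).

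**Assumptions.** Equal correlation ρ of 0.5 to 0.7 among the five ratings; a constant true difference; 2 or 4 participants lost, each missing weeks 2 and 4. The documents give none of these.

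**1. The plan's own figure.** Noncentrality = 10 / (6 × √(2/16)) = 4.71 on 30 df. Power is 99.5%, so the stated bound of more than 80% is met with a wide margin.

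**2. Ratings discarded (illustration).** If each of the three later visits is missed independently with probability q, expected completers are 32 × (1 − q)³: 27.4, 23.3 and 19.7 at q = 5%, 10% and 15%. At 10%, 160 − 0.1 × 96 ≈ 150 ratings are collected, and a complete-case analysis uses 23.3 × 5 ≈ 117. About 34 collected ratings go unused.

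**3. Precision, loss at random.** The SD of a person's five-rating mean is 6 × √((1 + 4ρ)/5): 4.65 at ρ = 0.5 and 5.23 at ρ = 0.7. The standard error of the difference is that SD × √(2/n).

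| | ρ = 0.5 | ρ = 0.7 |
|---|---|---|
| None lost (n = 16) | 1.64 | 1.85 |
| Two per arm lost, complete cases (n = 14) | 1.76 | 1.98 |
| Two per arm lost, likelihood model | 1.65 | 1.86 |

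The likelihood model recovers nearly all the lost precision. At an illustrative 5-point difference, simulated power is 78% / 69% (ρ = 0.5 / 0.7) for complete cases, 83% / 75% for the likelihood model, and 84% / 76% with nobody lost.

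**4. Bias, loss related to severity.** Simulated estimates of a true difference of 10, averaged over the five times, at ρ = 0.5 / 0.7. The Monte Carlo error is about 0.03 or less. The two-arm rule is logit p = a + 0.7 × (week 1 score / SD). Since e^0.7 ≈ 2, the odds of loss double per SD of worsening.

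| Pattern of loss | Lost | Complete cases | Likelihood model |
|---|---|---|---|
| Same rule, both arms | 2 in total | 9.86 / 9.88 | 9.99 / 10.06 |
| Same rule, both arms | 4 in total | 9.74 / 9.65 | 10.00 / 10.00 |
| Worst placebo participants at week 1 | 2 | 9.22 / 9.03 | 10.00 / 10.02 |
| Worst placebo participants at week 1 | 4 | 8.58 / 8.23 | 10.02 / 10.06 |
| Worst SNP participants at week 1 | 2 | 10.8 to 11.0 | 10.0 (by symmetry) |
| Worst SNP participants at week 1 | 4 | 11.4 to 11.8 | 10.0 (by symmetry) |
| Worst placebo participants at unseen week 2 | 2 | 9.16 / 9.06 | 9.75 / 9.92 |
| Worst placebo participants at unseen week 2 | 4 | 8.54 / 8.22 | 9.60 / 9.80 |

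The two-arm rule gives a small net bias because placebo participants score higher and so leave more often (about 2.9 against 1.1 when 4 are lost). With no true effect, losing the worst SNP participants gives the complete-case test a two-sided type I error of 8–9% (2 lost) or 14–17% (4 lost), in SNP's favour. When loss depends on the unseen week 2 score, the likelihood model removes most of the bias but not all.

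**5. Power at 10 points.** It stays at about 98.6% or more in every scenario with 2 or 4 lost.

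**6. Cost when nothing is missing.** At a 6-point difference and ρ = 0.6, the two methods gave the same estimate and the same power (91.6% each).

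**The case against.** The strongest objection is that the plan contains no deletion rule. Whole-person deletion is how the conventional method behaves; a long-format stratified ANOVA call in R would not strictly drop the participant, though its unbalanced decomposition is hard to interpret. This stands. A reader might infer that the plan prescribes complete-case analysis, but the documents support only that the handling is unstated.

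Second, loss may be small. Two of the five ratings fall on the supervised infusion day, follow-up lasts 28 days, the participants are "stable (not hospitalized) patients with early course schizophrenia", and entry requires "taking antipsychotic for 8 weeks with a stable dose of 4 weeks (no medication change will be allowed during the trial". This also stands: the size of the problem is set by assumption. Biases near or above 1 point need exactly the worst participants of one arm, and nobody from the other, to leave. Under the two-arm rule the bias is about 0.2 of a standard error at most.

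Third, a reader might assume that such bias is merely conservative. That holds only if sicker placebo participants leave from a trial with a true benefit. The mirror case favours SNP, and nothing in the documents makes one direction likelier.

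Finally, the simulations evaluate only the time-averaged difference, under a constant effect and equal correlations. They do not evaluate the group-by-time interaction.

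**Conclusion.** The point holds as a low-cost improvement. The primary analysis has no missing-data rule, and the named method in its usual form discards collected ratings. With 2 to 4 participants lost, SD 6 and correlation 0.5 to 0.7, the consequences are a standard error about 7% larger (two per arm at random: √(16/14) = 1.07), a bias of about 0.1 to 0.4 points if one severity rule acts in both arms, and at most about 0.8 to 1.8 points, in either direction, in the extreme one-arm cases.

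It would be tempting to conclude that the trial becomes underpowered. It does not: power for the planned 10 points stays far above 80%. Nor do the documents show that substantial or one-sided loss is expected.

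**What to change.** Replace the mixed ANOVA with a likelihood-based (REML) repeated-measures mixed model with treatment, time and their interaction, using every randomised participant and all observed PANSS ratings. Specify in advance:

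- a small-sample degrees-of-freedom correction, such as Kenward-Roger or Satterthwaite;
- an unstructured covariance, with a named fallback such as compound symmetry if it does not converge;
- the primary treatment contrast, for example the difference averaged over the five times or the difference at week 4;
- a table of missed PANSS ratings by arm and visit.

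Settle this before unblinding. It needs no added visits, ratings or participants. There are two downsides. An unstructured 5 × 5 covariance has 5 × 6 / 2 = 15 parameters for 32 people and may not converge, hence the fallback. And the model removes bias only when loss depends on observed ratings; loss driven by unseen scores leaves some, which is why missed ratings should be reported by arm.

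### The mixed ANOVA for PANSS and cognition comes with no analysis population and no missing-rating rule; as usually run it compares completers only, and the SNP effect can be biased in either direction

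*Combined protocol and SAP*

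**What the plan says.** B3.A (Outcome) sets the endpoint: "Primary outcomes include the change in PANSS positive and negative scores (2hrs, 5hrs, 1wk, 2wk, and 4wks"), SNP against placebo. Cognition is assessed at 0 h and at 1, 2 and 4 weeks. B3.B states that the primary outcome "will be analyzed using a 2 (treatment group) × 5 (time point) mixed analysis of variance (ANOVA"), with a 2 x 4 mixed ANOVA for cognition. It names R as the software but no routine.

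On completeness, B3.A says "All participants should complete their follow-up study visits". B5 (Psychological Interview) tells participants that "they will be able to withdraw from the study at any time". B5 (Protections Against Risks) refers a participant whose symptoms worsen for treatment, while B3.C allows no medication change during the trial. Nothing says whether such a participant is still rated, or whether later ratings count.

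The document gives no analysis population, intention-to-treat statement, missing-data rule, expected dropout rate or sensitivity analysis. Enrolment is 32 (B6) with no allowance for loss.

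**The concern.** A classical group-by-time ANOVA needs a full row per participant. Under the usual default, someone with four of five PANSS ratings contributes nothing, and someone who leaves after week 1 also loses the 2 h, 5 h and 1 week ratings already taken. The comparison is then no longer between the arms as randomised.

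If those who leave are those who worsen, the completers in an arm look better than the arm as randomised. The effect on the SNP-placebo difference depends on which arm loses more of them, so either a missed benefit or a spurious one is possible. With 16 per arm, a few people matter.

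**Working it through.** **1. The plan's own power figure.** B3.B claims: "With 16 ECS individuals in the SNP group and 16 in the placebo group we will have >80% power". Its inputs are a two-sample t-test, two-sided at the 5% level, an SD of 6 and a target of 10 PANSS points. The noncentrality is (10/6)/√(2/16) = 4.71 on 30 degrees of freedom, which gives power 99.5%. The stated figure holds as an inequality. The same t-test gives 98.3% with 13 per arm, 91.3% with 9 and 81.6% with 7.

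**2. How many participants are dropped.** The missing rate p per rating is assumed and taken as independent across ratings. The share with at least one gap is 1 - (1 - p)^k.

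| p | k = 5 (all ratings at risk) | of 32 | k = 3 (follow-up visits only) | of 32 |
|---|---|---|---|---|
| 2% | 1 - 0.98^5 = 9.6% | 3.1 | 1 - 0.98^3 = 5.9% | 1.9 |
| 5% | 1 - 0.95^5 = 22.6% | 7.2 | 1 - 0.95^3 = 14.3% | 4.6 |
| 10% | 1 - 0.90^5 = 41.0% | 13.1 | 1 - 0.90^3 = 27.1% | 8.7 |

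Ratings lost at p = 5%, k = 5: there are 32 x 5 = 160 scheduled ratings, of which 8 are missing. The 7.2 incomplete participants hold 7.2 x 5 = 36 slots. So 36 - 8 = 28 ratings that were observed are thrown away.

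**3. Bias of the completer comparison.** Simulation with very large arms, so that the results show bias and not sampling noise. Five correlated normal ratings with SD 6 (from B3.B); correlation either 0.6 throughout or first-order autoregressive 0.8; SNP effect the same at all times; participants leave after week 1 or week 2 if their change exceeds a threshold. Everything except the SD is assumed. Negative values favour SNP, and the completer estimate is averaged over the five times.

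| True effect | Who leaves when worse | Loss | Completer estimate |
|---|---|---|---|
| -5 | both arms, same rule, light (higher threshold or lower chance of leaving) | placebo 6-14% | -4.3 to -4.6 |
| -5 | both arms, same rule, heavy (above +3 with 50% or 100% leaving, or above +6 with 100%) | placebo 22-44%, SNP 5-15% | -3.1 to -4.1 |
| -5 | SNP only, light to heavy rules | SNP only | -5.1 to -6.2 |
| 0 | both arms, same rule | equal | 0 |
| 0 | SNP only | SNP only | -0.5 to -3.1 (false benefit) |

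A second set-up (correlation 0.6, 60% chance of leaving after any change above +4) gives the same pattern for a true -5: same rule in both arms -3.4, placebo only -2.4, SNP only -6.0, purely random loss -5.0. For a true 0 it gives -2.6 (SNP only) and +2.6 (placebo only).

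**4. The alternative.** A likelihood estimate from all observed ratings returned the true value in each of these second set-up scenarios (-5 or 0, to within about 0.05). It does so because simulated dropout depends only on ratings already observed.

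**The case against.** - **The plan does not say complete cases only.** True. B3.B names R and no routine, and some implementations keep incomplete participants in an unbalanced analysis. Dropping them is the likely default, not a certainty. What stands is that software behaviour, not the plan, would decide who is analysed.
- **The 2 h and 5 h ratings are well protected.** They fall within one supervised visit with staff assigned to the rating scales (B3.A, Infusion Considerations). This is fair, and it is why the three-visit column is shown. Withdrawals that remove several ratings at once would lower the share with a gap further.
- **The larger biases need heavy loss.** Also true. The -3.1 to -4.1 range takes 22-44% placebo loss in a four-week, single-infusion trial. With light loss the shortfall is about half a point.
- **Power survives.** Yes. Even at 10% missed per rating, about 9 per arm remain and power is 91.3% on the plan's inputs.

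Two stronger readings are tempting. A reader might infer that completer analysis pulls the SNP effect toward zero whenever those who worsen leave. That holds if SNP works and one leaving rule acts in both arms, or if the leavers are mainly on placebo. If they are mainly on SNP the estimate moves away from zero, and the document does not say which arm will lose more. A reader might also infer that a paused infusion costs the 2 h rating and so removes SNP participants selectively. No section says a pause cancels a rating; Phase I lasts 10 minutes, and most Phase II triggers first lower the dose. That route is conjecture.

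**Conclusion.** The point holds as an analysis-choice weakness that should be corrected. The named method, with no analysis population or missing-rating rule beside it, by default discards partly observed participants and gives up the randomised comparison. At the assumed missing rates the loss is between about 2 and 13 of 32. For a true -5 the bias runs from about half a point to nearly 2 points toward zero under a common leaving rule, or up to about 1.2 points away from zero if only worsening SNP participants leave. With no true effect, one-arm loss of those who worsen creates a spurious difference of about 0.5 to 3 points. If loss is unrelated to outcome, or there is no true effect and the rule is the same in both arms, there is no bias. These sizes rest on assumed missing rates, correlations and leaving rules. The omission itself is certain; the direction of any bias is not.

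**What to change.** **B3.B:** replace the mixed ANOVA for PANSS and cognition with a linear mixed model for repeated measures: categorical time, group-by-time interaction, unstructured covariance or a simpler one if it does not converge, and small-sample degrees of freedom. Fit it by REML to all available ratings of everyone randomised, whether or not the infusion was completed. Add a sensitivity analysis for dropout that depends on unobserved scores.

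**B3.A:** state that participants who stop the infusion are still asked for the remaining scheduled ratings. If these may be taken remotely, two sections must first be reconciled: B6 limits video procedures to screening and baseline, while B7 (Privacy) says some assessments can be virtual. Protocol and consent wording may then need to change.

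**Cost:** a few sentences and standard R code, plus any amendment for remote ratings. The downsides are that a covariance structure must be fitted on 32 participants, and that the likelihood model is unbiased only if dropout depends on observed ratings, which is why the sensitivity analysis is needed.
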